## Sensitivity Analysis examining impact of FDA order

A sensitivity of the primary analysis treatment group comparisons on the primary analysis population will be performed to assess any potential impact from the protocol amendment in response to the April 16, 209 FDA order removing transvaginal mesh from the market on primary efficacy. The analysis will be performed on the subset of participants treated before April 18, 2019. Patients excluded from the sensitivity analysis were told they would not be getting TVM prior to surgery, yet

each of these patients did consent to the 3-arm trial and will be treated under the revised protocol so they are not protocol violations. Results of the sensitivity analysis will be compared to those obtained from the primary efficacy analyses. Any important differences will be reported.

### **Sensitivity Analysis on Supportive Populations**

A sensitivity analysis of the primary outcome through the primary endpoint of 3 to a maximum of 5 years on the supportive population (as defined in section 5) for each of the 4 primary hypothesis tests will be conducted via the previously described PWE survival model using the same model parameterizations and covariate adjustments as the primary efficacy analysis. The supporting nonparametric survival model (described above) will also be fitted.

### Sensitivity Analysis without adjustment for site, or age category

A sensitivity analysis of the primary outcome through 3 to a maximum of 5 years on the primary analysis population will be conducted via the previously described PWE survival model, but only controlling for the randomized surgical intervention, with no adjustment for pooled site, or age category (all other model specifications will remain the same as the primary efficacy analysis).

## Sensitivity Analysis evaluating impact of missed visits due to COVID pandemic

A sensitivity analysis of the primary outcome through the primary endpoint of 3 to a maximum of 5 years on the primary analysis population will be conducted via the previously described PWE survival model, with an additional covariate controlling for the year of the participant enrollment, and also testing for the interaction between enrollment cohort and overall treatment effect. Since enrollment was over 3 years, and the last patients were enrolled in 2018, the year 1 cohort had impact of 2020 and 2021 pandemic at the end of their follow-up, and the last participants enrolled had this impact in earlier years of their enrollment.

### Sensitivity Analysis treating site as a random effect

A sensitivity analysis of the primary outcome through the primary endpoint of 3 to a maximum of 5 years on the primary analysis population will be conducted to assess impact of treating site as a random rather than fixed effect. Due to limitations of the methodology and SAS procedures for interval censored data, there is no direct option to model site as a random effect. Therefore, the sensitivity assessment will be completed as follows: as done for the primary SUPeR 3-year *JAMA* publication: First, we will fit the previously described PWE survival model, but instead of interval censoring we will right censor the failures at the midpoint of the interval (all other model specifications will remain the same as the primary efficacy analysis). We will confirm that this model produces essentially the same hazard ratio point and interval estimates and p-value as the primary interval censored model. Next, we will fit a second version of this same model as a frailty model moving site from a fixed effect to a random effect. We expect that the point estimates from the random site frailty model will be similar to the primary model, and the confidence interval to be slightly wider, resulting in a slightly larger p-value.

## 9.5 Secondary Efficacy Analysis Methods

### **9.5.1** Secondary Efficacy Outcomes

All secondary anatomical and functional efficacy outcomes are collected longitudinally across the study. All analyses for secondary outcomes are considered to be descriptive rather than inferential, so p-values will be interpreted as measures of evidence of descriptive differences in the treatment arms, not formal inferences.

For all secondary outcomes, point estimates and 95% confidence intervals for pairwise comparisons between each of the mesh repairs versus the native tissue repair as well as between the two mesh repairs will be obtained along with a p-value for the overall test assessing if any of the treatment effects are different. Treatment groups will be compared in the MITT population for all secondary efficacy outcomes.

Unless otherwise specified, all other secondary efficacy outcomes collected across multiple visits, analyses will include data only collected through 3 years (visits occurring after 3 years are excluded) using appropriate adjusted repeated measures models that account for subject correlations across visits. If the data corresponding to a secondary efficacy outcome is also collected at baseline prior to surgical intervention, these outcomes will be analyzed as change from baseline. Models will be adjusted for randomized surgical intervention, time in months as intended by the visit schedule, intervention by time interaction, baseline value, pooled site and age category consistent with study randomization design.

Treatment groups will be compared for any secondary efficacy outcomes evaluated in an aggregate fashion (e.g. proportion of participants with an event occurrence through 3 years), using a chi-square test or Fishers exact test for rare events. Additional details are provided in the specific sections below.

### **9.5.2** General Approach

As outlined in the above sections, the secondary outcome variables comprise a combination of binary, ordinal, and continuous measures that are repeatedly collected at post-operative visits. These outcome measures will be summarized in tabular fashion by treatment arm over the first 3 years of follow-up period. We will use model-based approaches appropriate for the variable type to compare the outcomes for the three treatment arms across time: linear mixed models for repeated measures (MMRM) for continuous variables and logistic generalized mixed models for repeated measures for binary efficacy outcomes. The few ordinal outcomes will either be analyzed in the same manner as continuous scores or otherwise dichotomized.

Because the primary scientific interest for the study is in the trajectories of the outcomes across time, a longitudinal approach incorporating **all post-operative time points through 3 years** will be employed for all repeated continuous assessment. Specifically, the unit of analysis will be the participant visit, where visits are defined as in Section 4.5 starting 6 months post operatively unless otherwise specified, and the models will incorporate treatment group, time, treatment group by time interaction, as well as pooled site and age category, the randomization stratification variables, and baseline value as fixed effects. Time (or visit) will be treated as a categorical variable to incorporate the expected non-linearity of time effects. The correlation structure between visits for a participant will be fit as an autoregressive AR1.

The general structure of the SAS code that will be used for the linear mixed model (using the POPDI-6 as an example) is summarized below.

Proc Mixed data=ASPIRe; WHERE visit le 36; \*\*\* Constrains analysis to first 36 months of follow-up; Class treatment visit pooledcenter agegroup participant;

Model POPDI-6_change = POPDI-6_baseline treatment visit treatment*visit pooledcenter agegroup/ DDFM=KR;
Repeated visit / type =AR1 subject=participant R RCORR;
Lsmeans treatment*visit/ pdiff CL;*** adjusted mean and adjusted mean difference estimates **;
Contrast 'POPDI change at Month 36: TVM vs SC' treatment 0 -1 1 treatment*month 0 0 0 0 0 0
0 0 0 0 0 -1
0 0 0 0 0 1;;
Contrast 'POPDI change at Month 36: TVM vs NTR' treatment -1 0 1 treatment*month 0 0 0 0 0 -1
0 0 0 0 0 0 0
$0\ 0\ 0\ 0\ 0\ 1$ ;
Contrast 'POPDI change at Month 36: SC vs NTR' treatment -1 1 0 treatment*month 0 0 0 0 0 -1
$0\ 0\ 0\ 0\ 0\ 1$
$0\ 0\ 0\ 0\ 0\ 0$ ;
CONTRAST '2 df trt grp comparison at Month 36: treatment -1 1 0 treatment*month 0 0 0 0 0 -1
0 0 0 0 0 1
$0 \ 0 \ 0 \ 0 \ 0 \ 0 \ 0 \ 0 \ 0 \ 0 \$
treatment -1 0 1 treatment*month 0 0 0 0 0 -1
0 0 0 0 0 0
$0\ 0\ 0\ 0\ 1$ ;

As suggested by the SAS code, the treatment groups will be tested using the F-test from the Contrast statements, which test whether mean change in POPDI at 36 months differs for each of the pairwise comparisons of the surgical arms of interest, as well as the overall 2 degree of freedom test comparing the 3 treatments at 36 months. The LSMEANS statement will provide by-visit estimates of the post-operative POPDI6 change score for each treatment arm from Month 6 through Month 36. These estimates will allow a description of the difference in trajectory of treatment effect in the pairwise comparisons of the surgical arms of interest and will provide descriptive measures of differences between the pairwise comparisons of the surgical arms of interest at each study visit.

If the repeated outcome is binary rather than continuous (such as Apical Descent  $C > -2/3 \times TVL$  at each visit), a generalized linear mixed model will be used in the analysis. The SAS procedure GLIMMIX will be used with a binomial distribution and an identity link to generate comparable comparisons between the treatment arms using a risk difference rather than a mean difference.

```
Proc GLIMMIX data=ASPIRe;
WHERE visit le 36; *** Constrains analysis to first 36 months of follow-up;
NLOPTIONS TECHNIQUE=nrridg;
Class treatment visit pooledcenter agegroup participant;
Model dependent variable = treatment visit treatment*visit pooledcenter agegroup/ DIST=BIN, Link=Identity DDFM=KR;
Random visit / type =AR1 subject=participant RSIDE;
Lsmeans treatment*visit/ DIFF CL; *** adjusted event rate estimates and adjusted risk difference estimates **
*** code assumes treatment group takes values NTR, SC, TVM ***;
ESTIMATE 'risk difference at Month 36: TVM vs SC' treatment 0 -1 1 treatment*month 0 0 0 0 0 0
                                                                                      00000-1
                                                                                      000001/CL;
ESTIMATE 'risk difference at Month 36: TVM vs NTR' treatment -1 01 treatment*month 00000-1
                                                                                       000000
                                                                                       000001/CL;
ESTIMATE 'risk difference at Month 36: SC vs NTR' treatment -1 1 0 treatment*month 0 0 0 0 0 -1
                                                                                      000001
                                                                                      00000/CL;
CONTRAST '2 df trt grp comparison at Month 36: treatment -1 1 0 treatment*month 0 0 0 0 0 -1
                                                                              000001
                                                                              000000,
                                              treatment -1 0 1 treatment*month 0 0 0 0 0 -1
                                                                              000000
                                                                              000001;
```

If this does not converge, we will change to a simpler compound symmetric covariance structure. If the model does not converge, then we will simplify further by removing pooled site and then age category from the model. If this model does not converge, we will conduct an unadjusted chi-square analysis for risk differences using the 3-year timepoint data, as described for binary outcomes below

Treatment groups will be compared for any secondary efficacy outcomes evaluated in an aggregate fashion as opposed to by visit (e.g. proportion of participants with an event occurrence through the final visit), using an unadjusted chi-squared tests or Fisher's exact tests for rare events with expected cell counts < 5. Risk differences with 95% CIs are based on Mantel-Haenszel estimates for the risk difference with Wald-type CIs. For events with expected cell counts < 5, the exact risk difference and 95% CI are obtained by exact methods based on the score statistic based on Chan and Zhang (ref Chan, Zhang 1995). Where specified, Binomial 95% CIs for proportions are based on the exact Clopper-Pearson method (ref Clopper, Pearson).

In SAS, using PROC FREQ:

The site and age group adjusted mantel-Haenszel chi-square test and risk difference with CIs using Wald-type variance under the null hypothesis as specified by Sato are obtained by:

table poolediste\*agegrp\*trtgrp\*outcomevar / riskdiff (COMMON) (METHOD=WALD EQUAL VAR=NULL ) CMH;

The unadjusted chi-square test and risk difference with CIs using Wald-type variance under the null hypothesis as specified by Sato are obtained by:

table trtgrp\*outcomevar / riskdiff (METHOD=WALD EQUAL VAR=NULL) CHISQ CMH;

The unadjusted exact test and score risk difference CIs are obtained by:

table trtgrp\*outcomevar / FISHER; exact riskdiff (METHOD=SCORE);

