#### 7.6 Multisite Studies

This study is conducted in nine sites in the Pelvic Floor Disorders Network. For this multisite study, randomization of study participants was stratified within site. Consequently, for all model-based primary and secondary analyses, site will be included as a fixed effect in the models.

Pooling of sites is defined as grouping the subjects from one or more sites together and considering these subjects as representing a single site for the purpose of summary and analysis. The purpose of pooling is to ensure that each site contains a sufficient number of subjects for sample size requirements of statistical analysis methods that consider site as a factor.

For all statistical analyses, sites with fewer than 25 randomized patients will be pooled based on geographical location. Specifically, UCSD (n=17) and sub-site Kaiser-Downey (n=11) will be pooled with Kaiser- San Diego (n=61), New Mexico (n=1) will be pooled with UTSW (N=26), and Cleveland Clinic (n=3) will be pooled with University of Pittsburg (N=25), resulting in 7 pooled sites.

As a supplemental analysis associated with the primary outcome, we will examine descriptively whether the treatment effect varies across pooled sites; however, no other analyses will assess site differences in treatment effect because sample sizes are inadequate to support evaluation of site-level effects.

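### SAP 9.5.2 names two different links for the repeated binary secondary outcomes, and the identity link is prone to fail for rare or very common outcomes, which sends the analysis down a fallback that removes randomisation strata

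*SAP*

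**What the plan says.** SAP 9.5.2 covers secondary outcomes collected repeatedly through 36 months. Its opening paragraph assigns "logistic generalized mixed models for repeated measures for binary efficacy outcomes". Further down, for outcomes such as apical descent (point C above -2/3 TVL), it says "The SAS procedure GLIMMIX will be used with a binomial distribution and an identity link", on the ground that the result is then a risk difference. The code agrees with that second statement: "Model dependent variable = treatment visit treatment*visit pooledcenter agegroup/ DIST=BIN, Link=Identity DDFM=KR".

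The fallback is a ladder:

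1. "If this does not converge, we will change to a simpler compound symmetric covariance structure". Site and age stay in.
2. If that fails, "then we will simplify further by removing pooled site and then age category from the model".
3. If that fails, "we will conduct an unadjusted chi-square analysis for risk differences using the 3-year timepoint data".

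SAP 7.6 says that "for all model-based primary and secondary analyses, site will be included as a fixed effect in the models". Protocol M.3 likewise asks for the randomisation stratification factors in every model-based analysis. Those factors are site (7 pooled sites in the analysis) and age under 65 versus 65 or over. SAP 9.5.1 declares all secondary analyses descriptive. SAP 10.3 carries the same mixed models over to any safety outcome analysed as repeated measures.

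**The concern.** The section gives two links for the same outcomes. The one that is coded constrains every fitted risk to lie between 0 and 1 while adding site and age effects directly to the risk. For a rare or very common outcome there is little room for such effects. The fit then fails for a reason that the first fallback step does not address, because changing AR(1) to compound symmetry leaves the mean model as it was. The next step removes a stratification factor.

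At stake is whether by-visit results for apical descent and similar outcomes, which the protocol places in the primary manuscript, are adjusted as the plan promises. They could instead be reported from whichever step converges, with different adjustment for different outcomes. The last step also uses month 36 alone. SAP 7.3 places the pandemic period, with remote visits lacking a POP-Q, in March 2020 to July 2022. The E-ASPIRe addendum implies a first surgery around March 2016, and the last was in June 2019. Month-36 visits for surgeries from about March 2017 onward therefore fall in that period.

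**Working it through.** **No planned figure.** The documents give no expected event rate or convergence rate for these outcomes, so there is nothing to reproduce. The rates below are assumptions, shown over a range.

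**What the documents suggest for apical descent.** Protocol Appendix A, Table 7 lists, for the CARE trial at two years after sacral colpopexy (SC), 95% with point C within 2 cm of TVL. That means C ≤ -(TVL - 2). When TVL ≥ 6 cm (the entry requirement), TVL/3 ≥ 2, so C ≤ -(TVL - 2) implies C ≤ -2/3 TVL. An SC risk of about 100% - 95% = 5% or lower is therefore plausible, although it comes from another trial.

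**Why the fit is fragile.** The coded mean is

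risk = α(arm, visit) + σ(site) + γ(age).

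With six visits to month 36 this has 3 × 6 + 6 + 1 = 25 parameters. Up to 3 × 6 × 7 × 2 = 252 fitted risks must all lie inside (0, 1).

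- At an SC risk of 5%, a combined site and age effect of -5 points takes the fitted risk to zero.
- A visit-specific SC risk with 121 women has standard error √(0.05 × 0.95/121) = 2.0 points, so the lowest of six visits will often be estimated below 5%.
- A pooled site of 28 women (25 + 3 in SAP 7.6) at an overall risk of 10% has standard error √(0.10 × 0.90/28) = 5.7 points at one visit. Even if six visits were independent it would be 5.7/√6 = 2.3 points.

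Sampling error alone is thus of the same order as the room available.

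**Simulation.** There were 363 women, 6 visits, 7 pooled sites and the 25-parameter mean. Assumed: the sizes of four pooled sites, half the women aged 65 or over, native tissue log-odds 0.6 higher, latent AR(1) correlation 0.8, and missing data rising 3% per visit. Ranges span two scenarios: no site or age effect; and site SD 0.3 logits with age odds ratio 1.3. AR(1) columns use 24 trials per scenario; the interior-maximum and logit columns use 30. The largest Monte Carlo standard error is √(0.25/24) = 10 points.

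| Reference risk | Identity, site + age, AR(1): valid fit | Identity, site + age, independence: maximum inside (0, 1) | Identity, site dropped, AR(1) | Identity, site and age dropped, AR(1) | Logit, site + age, independence: finite estimates |
|---|---|---|---|---|---|
| 3% | 0% | 0% | 21-29% | 92-96% | 40-53% |
| 5% | 4% | 0% | 42-62% | 92-96% | 80-83% |
| 10% | 0-12% | 20-33% | 100% | 100% | 97-100% |
| 15% | not run | 53-63% | not run | not run | 100% |
| 20% | 62-75% | 77-83% | 100% | 100% | 100% |
| 30% | 88-92% | 90-93% | 100% | 100% | 100% |

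**Cross-checks under other assumptions.** Two further simulations used working independence.

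- The first had a within-woman SD of 1.5 logits, 10% missed visits and 60 trials per setting. With SC 5%, TVM 10%, NT 20%, fitted risks left (0, 1) in 98% of trials, and a constrained fit ended on the boundary in 20 of 24. With 10/15/30% they left it in 38-80%. For an improvement outcome such as PGI-I they left it in 43-78% at 85-90% and in 18-25% at 75-85%. A logit fit converged in 90-100%.
- The second found the identity fit valid in 11% of trials at 5/10/20%, 45% at 10/15/30%, 55% at 85-90%, and 85-99% at moderate rates. Dropping site alone restored 93-100%. A logit fit with the same terms converged in 96-100%.

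All three agree in direction. They differ on whether dropping site is enough: it is at 10% or more, or with an arm mix such as 5/10/20%, but often not when all arms sit near 3-5%.

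**The case against.** The strongest reply has five parts.

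- **The specific text governs.** Both the later prose and the code specify the identity link and say why, so an analyst would know which to run. This is fair. A reader might see a clash of text with code, but the conflict is between two statements within 9.5.2, and the first could be cured by changing one word. That would still leave the fragile model in place.
- **Failure is not general.** A reader might infer that the identity-link model usually has no valid solution. The documents give no rates that would support this, and at 20-30% most simulated fits succeed.
- **The ladder is ordered in advance and does not drop both strata at once.** Correct. Compound symmetry with both strata comes first, then site goes, then age. Losing age as well is mainly a matter of very low rates.
- **The consequence is modest.** These outcomes are descriptive. The risk difference is collapsible and arms are randomised, so omitting site or age mainly costs precision and does not change the target. SAP 7.2 speaks only of most efficacy analyses, and a chi-square is not model-based. This stands, but the reduced GLIMMIX models still conflict with SAP 7.6 and Protocol M.3.
- **The evidence is approximate.** SAS GLIMMIX, with its pseudo-likelihood and the ridge-stabilised optimiser named in the code, was not run. This also stands: the percentages show direction and rough size only.

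**Conclusion.** The two statements of the link in SAP 9.5.2 cannot both hold, and the coded choice is poorly suited to outcomes with risks of about 10% or lower, or about 90% or higher. For apical descent at a rate near 5% in an arm, the full identity-link model reached a valid fit in 11% of simulated trials or fewer, so following the plan would probably remove site from its own example. For outcomes at roughly 20-80% the model usually fits and the concern largely falls away.

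The damage is limited to precision and to consistency of adjustment across descriptive secondary results. The primary time-to-failure analysis uses a different model and is not affected. The conclusion rests on assumed event rates, some assumed site sizes and an approximation to GLIMMIX.

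A reader might also infer that 9.5.1 already requires baseline point C in the apical-descent model. It asks for the outcome's baseline value. For this indicator that value is constant, because every woman had to have C above -2/3 TVL at entry. Continuous baseline point C would be an optional extra covariate.

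**What to change.** - State one model in 9.5.2: binomial with a logit link, and arm, visit, arm by visit, pooled site and age category as fixed effects.
- Obtain the risk difference at each visit by marginal standardisation, averaging predicted risks over the observed site and age mix, with delta-method or bootstrap confidence intervals. The estimand stays the one the plan wants.
- Delete the steps that remove site and age. On non-convergence, simplify the covariance first. If that fails, use the site- and age-stratified Mantel-Haenszel risk difference, for which 9.5.2 already has PROC FREQ code. A terminal fallback is needed because the logit model also separates at very low rates (finite estimates in 40-53% of simulated trials at 3%).
- Keep unadjusted exact methods only for events too sparse for the stratified estimate.
- Report which step was used for each outcome.
- Adding continuous baseline point C for apical descent is optional.

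The cost is SAP wording and a short macro. No data collection or primary analysis changes.

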NCI recognized the limitations of the CTCAE in capturing symptomatic AEs and has worked to significantly expand the scope of the CTCAE through direct integration of the patient perspective starting in 2008. [9] A consortium was established with the goal of developing a standardized measurement system that can accurately and reliably detect events from the patient perspective and the system is called the PRO-CTCAE. The PRO-CTCAE was developed with the capacity for investigators to select relevant items to generate tailored patient surveys and to schedule and electronically administer those surveys to participants via web or automated telephone IVR. 78 items from the CTCAE were identified as being amenable to self-reporting by adults with cancer and these are the AEs that are currently in the PRO-CTCAE version 1.0 library. NCI has made significant strides in the development of the PRO-CTCAE, although it is currently in testing format. Furthermore, the included adverse symptoms are most relevant to cancer trials and the majority are not relevant to pelvic floor disorders.

3.4. Need for PPAR:

Currently, AE symptom reporting is burdensome and time consuming for research staff and investigators. It is also inefficient especially when it is unclear which events are relevant to patients. The measurement and monitoring of AEs is often imprecise and of uncertain validity, but it is a fundamental piece of treatment evaluation. Even with using the CTCAE as a guide, reporting can be variable in terms of "grade" and "expectedness" between sites as well as within the same type of AE (e.g. findings from the SUPeR AE Adjudication Task Force). The SUPeR AE Adjudication Task Force was developed to help improve the consistency and reliability of AE reporting between clinical sites for the SUPeR trial, however we are still missing the patient perspective. Addressing this gap will help inform the relevance and impact of AEs from the patient perspective and guide and streamline future reporting for complications specific to pelvic reconstructive procedures.

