## **10.3** Secondary Safety/Tolerability Outcomes

In general, data for all secondary safety/tolerability outcomes are collected longitudinally across the study on complication tables at each visit and systematic collection of open-ended adverse events reported on the AE log. Secondary safety/tolerability outcomes are generally reported as a binary outcome evaluated in an aggregate fashion (e.g. through 5 years).

Treatment groups will be compared for binary safety outcomes using unadjusted chi-squared tests or Fisher's exact tests for rare events with expected cell counts < 5.. Risk differences with 95% CIs are based on Mantel-Haenszel estimates for the risk difference with Wald-type CIs. For events with expected cell counts < 5, the exact risk difference and 95% CI are obtained by exact methods based on the score statistic based on Chan and Zhang (ref Chan, Zhang 1995). Where specified, Binomial 95% CIs for proportions are based on the exact Clopper-Pearson method (ref Clopper, Pearson). These are the same methods as used for aggregate binary efficacy outcomes.

Maximum dindo score will be analyzed as an ordinal outcome with an unadjusted Mantel-Haenszel chi-squared mean score test with standardized midranks scoring (MODRIDIT option in SAS).

For any continuous or binary safety outcomes measured and analyzed as repeated measures, the same Mixed models as specified for efficacy assessments will be used. Continuous or ordinal safety outcomes assessed at a single timepoint, mean differences, 95% CIs, and *P* values are unadjusted and based on *t* tests for normally distributed continuous outcomes, and *P* values for non-normal continuous outcomes (summarized with medians) are from Wilcoxon Rank Sum tests.

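### Non-rare aggregate binary outcomes are tested without the randomisation strata, and the SAP does not say which call gives their risk-difference interval: low severity, nearly free to fix

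*SAP*

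**What the plan says.** SAP 4.3 and Protocol H.1 describe permuted blocks stratified by site and by age (under 65, or 65 and over). SAP 7.6 notes that "randomization of study participants was stratified within site" and on that ground puts pooled site into all model-based analyses. Protocol M.3 likewise requires the stratification terms in model-based analyses, and SAP 7.2 says most efficacy analyses will carry them.

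Outcomes counted once per participant over follow-up are not modelled. For efficacy, SAP 9.5.2 compares arms "using an unadjusted chi-squared tests", or Fisher's exact test where expected counts are below 5. For safety, SAP 10.3 states: "Treatment groups will be compared for binary safety outcomes using unadjusted chi-squared tests or Fisher's exact tests for rare events". Beside the efficacy test SAP 9.5.2 places an interval: "Risk differences with 95% CIs are based on Mantel-Haenszel estimates for the risk difference with Wald-type CIs". SAP 10.3 repeats that sentence. Neither section names strata at that point.

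The code at the end of SAP 9.5.2 then lists three PROC FREQ calls:
- a table stratified by pooled site and age group, with a common risk difference and a CMH test;
- an unstratified table, with chi-square and its own risk difference;
- an exact unstratified version.

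No text assigns the first or second call to the aggregate outcomes. A stratified Mantel-Haenszel risk difference is specified in words only for the cross-sectional surgical-failure analysis in SAP 9.4.3, event rates permitting.

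**The concern.** When treatment is balanced within strata that predict the outcome, between-stratum variation drops out of the treatment difference, but the crude standard error still includes it. The crude test then rejects too seldom under the null and has slightly less power than it could.

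The outcomes on this route include retreatment, incontinence recorded as an adverse event, urinary tract infection and pelvic pain. Some of them may depend on local practice. Protocol Appendix B, 3.4, says that adverse event "reporting can be variable in terms of" grade and expectedness between sites.

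The second issue is specification. With a single stratum, a Mantel-Haenszel risk difference is simply the crude difference, so the label adds something only if strata are meant. As written, two analysts could print different intervals beside the same p-value.

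**Working it through.** **The plan's own figures.** The SAP gives none for these tests. Its design figure for the primary outcome reproduces. The hazards are −ln(0.80)/2 = 0.1116 and −ln(0.65)/2 = 0.2154, a ratio of 1.93. With 2 years' accrual, 3 years' further follow-up and 5% annual loss, 242 participants give 79 events and 85.1% power at one-sided 0.03, against 85% stated. Nothing below affects it.

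**Inputs from the documents.** About 121 per arm. Strata: 7 pooled sites × 2 age groups = 14. SAP 7.6 gives three pooled groups of 89, 27 and 28. The share aged 65 or over is 39% (Appendix C projection). The 15-point difference is the guideline for important complications in Protocol N.4.

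**Assumed.** 20% event rate; block size 6; the other four sites at 55 each (364 in total); site effects on the logit scale of k × (−1.35, −0.76, −0.35, 0, 0.35, 0.76, 1.35); an age log odds ratio of k.

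**Analytic check.** If the strata explain a share R² of the outcome variance, the true size of the crude test is 2[1 − Φ(1.96/√(1 − R²))]. For R² = 0.116, 1.96/√0.884 = 2.085, which gives 0.037.

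**Simulated size**, 6,000 trials per row, two-arm comparison at two-sided 5% (Monte Carlo SE √(0.05 × 0.95/6000) = 0.003). The site range is the inverse logit of logit(0.20) ± 1.35k.

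| k | Risk, lowest to highest site | R² | Analytic size | Chi-square | CMH |
|---|---|---|---|---|---|
| 0 (none) | 20% | 0 | 0.050 | 0.052 | 0.052 |
| 0.3 (mild) | 14–27% | 0.014 | 0.048 | 0.047 | 0.046 |
| 0.5 (moderate) | 11–33% | 0.038 | 0.046 | 0.045 | 0.049 |
| 0.9 (strong) | 7–46% | 0.116 | 0.037 | 0.038 | 0.049 |

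**Power for a 15-point difference**, chi-square against CMH: 0.749 and 0.747 (none), 0.748 and 0.755 (moderate), 0.733 and 0.762 (strong). The gain is therefore about 0, 0.8 and 3.0 points.

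**Agreement of test and interval.** Let d be the crude difference and SE₀ = √[p̄(1 − p̄)(1/n₁ + 1/n₀)]. Pearson's statistic is (d/SE₀)². The unstratified call in SAP 9.5.2 is described as using the null variance, so its interval d ± 1.96·SE₀ excludes zero exactly when the test rejects. The two disagreed in 0% of trials. Chi-square set against a site- and age-stratified Mantel-Haenszel interval (Sato variance) disagreed in 0.8–1.6% of null trials and 1.4–4.6% of trials with a 15-point difference.

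**The case against.** Three stronger readings are tempting, and the documents do not support them.

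- *All binary safety outcomes are affected.* They are not. Rare events go to Fisher's exact test, and SAP 10.3 adds: "For any continuous or binary safety outcomes measured and analyzed as repeated measures, the same Mixed models" as for efficacy, which adjust for pooled site and age. The two PISQ-IR dyspareunia indicators in SAP 9.3 are defined visit by visit, so they fit the adjusted model too.
- *The tests are conservative, full stop.* Only if site or age is prognostic. The documents give no between-site event rates. Appendix B speaks of variable grading and expectedness, with experience from another trial as its example, not of differing incidence.
- *The printed p-values and intervals conflict.* The unstratified call pairs a test with its matching interval, and the stratified call has an evident home in SAP 9.4.3. A conflict arises only if an analyst takes the interval from the stratified call and the test from the other.

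Nor does SAP 7.6 contradict itself. Its rule covers model-based analyses, as Protocol M.3 does, so leaving simple tables unadjusted is a consistent choice. SAP 7.7 makes secondary p-values and intervals descriptive, so no formal decision depends on them.

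All of this stands and keeps the severity low. It does not remove the point. The plan gives no reason for dropping the strata here, already contains the stratified method, and leaves the source of the interval open for results meant for the primary manuscript.

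**Conclusion.** The point holds as a low-severity, nearly free improvement. It concerns aggregate binary efficacy and safety outcomes with expected counts of at least 5. Their chi-square tests are valid. Over the assumed range of strata effects their true size is about 0.038 to 0.052, and 0 to 3 points of power are given up for a 15-point difference, with no loss if the strata are not prognostic. The upper end of the loss needs site risks as far apart as 7% and 46% together with a sizeable age effect.

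Separately, SAP 9.5.2 is ambiguous about which call produces the interval. That is a gap in specification, not a demonstrated inconsistency. The primary model already adjusts for pooled site and age (SAP 9.4.2), so the primary tests, the alpha split and the sample size are unaffected.

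**What to change.** In SAP 9.5.2 and 10.3, state that for aggregate binary outcomes with expected counts of at least 5 both the p-value and the interval come from one analysis: the CMH test and the Mantel-Haenszel common risk difference, stratified by pooled site and age, in line with the stratified risk difference in SAP 9.4.3. Keep the exact unadjusted methods for rare events, and label each PROC FREQ call with the outcomes it serves.

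The cost is a few sentences, since the stratified call is already written. Two technical notes:
- A stratum with no events adds nothing to the CMH statistic, but it keeps its weight n₁n₀/N in the common risk difference and contributes a difference of zero. That is acceptable, but it should be known.
- The CMH test and a Sato-variance interval use different variances, so rare borderline disagreements can remain. With strong strata effects their null rejection rates were 0.049 and 0.051.

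If the team prefers to stay unadjusted, it should say so, name the unstratified call as the source of both figures, and drop the Mantel-Haenszel label.
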